### 6.3 SUBJECT SETS ANALYSED

The following patient sets are defined

- *Screened Set (SCR)*  
Consists of all patients screened for the trial, with informed consent given and who completed at least one screening procedure at Visit 1.
- *Randomised set (RS)*  
This patient set includes all randomised patients, whether treated or not.
- *Treated set (TS)*  
This patient set includes all patients who were dispensed study medication and were documented to have taken at least one dose of investigational treatment.
- *Treated Set-Follow-up (TS-FU)*  
All patients in the TS, for whom a follow-up visit was performed (i.e. values of planned assessments- KCCQ, EQ-5D, vital signs or lab data reported) between 23 and 45 days after last intake of study medication.

The TS-FU does not include patients, where no planned measurements were taken, which may happen in case of telephone FU visits. Patients with intake of open label SGLT-2 inhibitor between their EOT and FU visit are also excluded from the TS-FU set.

- *Pharmacokinetic Set (PKS)*  
This patient set includes all evaluable patients of the treated set who provide at least one observation for at least one further PK endpoint of Cpre,ss,N for empagliflozin.

### 6.4 SUBGROUPS

Subgroups to be considered in the analyses are provided in [Table 6.4: 1](#). Missing categories for subgroup variables will not be considered in the respective analysis.

If there is missing information for any of the subgroups, where data is also collected in the IRT system, then the information as transferred from IRT will be used to assign a patient to a certain category.

Although several subgroup analyses are prespecified in Table 6.4: 1, the subgroup analysis by Diabetes at baseline (diabetic, non-diabetic) is the medically and academically most important subgroup analysis.

Table 6.4: 1 Categories of covariates for displays of baseline characteristics and subgroup analyses

Variable	Categorization	Demo-graphics 	Subgroups for Efficacy endpoints 	Safety 
Diabetes at baseline	diabetic, non-diabetic	X	X	X (except ketoacidosis and hypoglycaemia)
	non-diabetic (Pre-diabetes, normal (no pre-diabetes)), diabetic (type 2 diabetes, type 1 diabetes)	X		X (Ketoacidosis and hypoglycaemia)
Age (years)	<50	X		X
	50 to <65			
	65 to <75			
	75 to <85			
	>= 85			
	<50	X		
	50 to <65			
	65 to <75			
	>= 75			
	< 65	X	X	
	≥65			
Sex	male	X	X	X
	female			
Region	NA, LA, Europe, Asia, Other +	X		X (overall  only)
Ethnicity	Hispanic/ Latino Not Hispanic/ Latino	X		X (overall  only)
Race	White Black/ African-American Asian Other including mixed race	X	X	X
BMI (kg/m  )	<30	X	X	
	≥30			

Table 6.4: 1 Categories of covariates for displays of baseline characteristics and subgroup analyses (cont.)

Variable	Categorization	Demo-graphics 	Subgroups for Efficacy endpoints 	Safety 
eGFR at baseline	>=90	X		
	60 to <90			
	45 to <60			
	30 to <45			
	20 to <30			
	<20			
	>=90	X		X
	60 to <90			
	45 to <60			
	30 to <45			
	<30			
	>=60	X	X	
UACR	<60			
	UACR (in mg/g):	X		
	<30			
	>=30 to <=300			
	>300			
History of hypertension	Yes / No	X		
Baseline SBP	< / >= median			
Baseline BP	SBP<140 and DBP<90 vs. SBP>= 140 or DBP>=90	X		X (volume depletion AEs and hypotension AEs)
Atrial Fibrillation at baseline\$	Yes/ No	X		
History of Atrial Fibrillation\$\$	Yes/ No	X		
Baseline LVEF	<20, >=20 to <=30, >30 to <=35, >35	X		
History of valvular disease	Yes / No	X		
History of HHF (in the last 12 months)	Yes / No	X	X	

Table 6.4: 1 Categories of covariates for displays of baseline characteristics and subgroup analyses (cont.)

Variable	Categorization	Demo-graphics 	Subgroups for Efficacy endpoints 	Safety 
Cause of HF	Ischemic Hypertensive Valvular heart disease Diabetic Alcoholism Idiopathic Other	X		
	Ischemic Non-ischemic		X	
Time since diagnosis of HF	<= 1 year, 1-5 years, > 5 - 10 years, >10 years	X		
NYHA at baseline	I/II/III/IV	X		
	II vs. III/IV		X	
Heart failure physiology	LVEF ≤ 30% and NT-proBNP < median  ; LVEF ≤ 30% and NT-proBNP ≥ median  ; LVEF > 30%		X	
Baseline use of ACE-inhibitor, ARB or ARNi	Yes / No	X#		X (renal AEs, volume depletion AEs and hypotension AEs)
Baseline use of MRA	Yes / No	X#	X	
Baseline use of diuretics	Yes / No	X#		X (renal AEs, volume depletion AEs and hypotension AEs)
Baseline use of loop or high-ceiling diuretics	Yes / No	X#		X (renal AEs, volume depletion AEs and hypotension AEs)
Baseline use of ARNi	Yes / No	X#	X	X (renal AEs, volume depletion AEs and hypotension AEs)

 The column demographics shows categories shown in the overall demographics. Demographics are not planned by subgroup.

 Subgroups planned for the primary endpoint, time to cardiovascular (CV) death, time to first HHF, HHF (first and recurrent), renal slope.

 X means subgroups planned for overall AE summaries, AEs by SOC and PT, SAEs, AEs leading to discontinuation, decreased renal function, UTI, genital infection, volume depletion, hypotension and bone fracture.

 Overall means overall AE summaries, AEs by SOC and PT, SAEs and AEs leading to discontinuation

 Median calculated separately for baseline atrial fibrillation or atrial flutter (determined by ECG) / no baseline atrial fibrillation and atrial flutter (determined by ECG)

+ Region categorization: see [Table 9.1.1](#).

# part of the presentation of baseline concomitant therapy as outlined in section [Section 7.2](#)

\$ atrial fibrillation at baseline: atrial fibrillation reported in last ECG before treatment intake

\$\$ history of atrial fibrillation: atrial fibrillation reported in any ECG before treatment intake or history of atrial fibrillation reported as medical history.

Additional subgroup analyses for specific further endpoints are defined in [Section 7.6](#)

## **6.5 POOLING OF CENTRES**

This section is not applicable because centre/country is not included in the statistical model.

## **6.6 HANDLING OF MISSING DATA AND OUTLIERS**

### **6.6.1 Imputation methods**

There will be no imputation of data for safety analyses. For patients who discontinue the trial treatment prematurely, all efforts will be made to follow patients for survival and for any other endpoints including the primary and key secondary endpoints until the end of the trial.

There will be different methods of looking at continuous longitudinal data.

#### Observed case on-treatment (OC-OT):

Only the available data that were observed while patients were on study medication (defined as time from first drug intake until last permanent treatment stop date plus the endpoint specific follow-up time (as defined in [Table 6.1:2](#)) are considered.

Measurements are assigned to planned weeks according to [Table 6.7: 1](#)

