7.5 HANDLING OF MISSING DATA

There will be no imputation for safety data or for time-to-event type of endpoints. For patients who discontinue the trial treatment prematurely, all efforts will be made to follow the patients for survival and any other endpoints, including the primary and key secondary endpoints, until the end of the trial.

For the slope analysis of eGFR (CKD-EPI)_{cr}, all available on-treatment change from baseline data will be used. Patients without on-treatment data after randomisation will not be included in this analysis.

For the analysis of change from baseline to 30 days after treatment stop, only available data will be used. Only patients with post-treatment data will be used in this analysis.

For other longitudinal efficacy endpoints such as KCCQ scores, MMRM methodology will be used. Models will be run on both all observed data and all observed on-treatment data. Details of the imputation rule will be given in the statistical analysis plan.

An eGFR (CDK-EPI) reduction is considered sustained, if it is determined by two consecutive post-baseline central laboratory measurements separated by ≥ 30 days. If only one post-baseline value is available and the patient dies within 60 days of this measurement without second measurement ≥ 30 days after the first, then the eGFR reduction is also considered sustained.

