## 6. GENERAL ANALYSIS DEFINITIONS

### 6.1 TREATMENTS

There will be 4 basic treatment phases in this trial: screening, study treatment phase (with either empagliflozin 10mg or matching placebo), post-treatment and post-study. However, during the study treatment phase, patients are allowed to go off-treatment and subsequently re-start treatment. This may happen not at all or repeatedly for a given patient.

The purpose of the definitions below is to describe all the different study/treatment intervals, in which a patient can lie during the course of the trial. Note that the term "treatment regimen" also covers the "off-treatment" time periods.

Table 6.1: 1 Treatment regimens / study intervals

Label	Interval	Start date
Screening	Screening	Date of informed consent
Placebo/ Empagliflozin 10mg	Treatment	Date of first administration of double-blind study treatment
Off-treatment (if applicable)	During Treatment interval, but not on treatment	Date of last administration of the study medication before temporarily discontinuation + 1 day
Placebo/ Empagliflozin 10mg (if applicable)	During Treatment interval, after restart of study medication	Date study medication re-started
Post-treatment	Post-treatment	Date of last administration of study drug + 1 day
Post-study	Post-study	Date of trial completion +1 day

Details on the definition of on-treatment period for different endpoints are listed in [Table 6.1:2](#). The efficacy analyses will follow the intention-to-treat (ITT) principle in assigning patients to treatment groups, i.e. patients will be analysed as randomised.

Safety analyses will also assign patients to the treatment group as randomized.

If a patient erroneously receives the wrong trial drug, all subsequent medication packs dispensed to the patient will still be for the treatment group to which the patient was randomized. Therefore the adverse events will be analyzed as per randomized treatment, which is expected to reflect the prevailing treatment.

In the exceptional case that a patient took the wrong treatment, adverse events may occur while being on the wrong treatment. Analyses of this data are described in [Section 7.8.1.6](#).

Table 6.1: 2 Endpoint specific assignment to the on-treatment phase

Endpoint	Last day of assignment to the on-treatment phase (days after last intake of study medication)
Adverse events	7
Safety laboratory measurements, including Urine Albumin Creatinine Ratio (UACR)	3
Heart rate	1

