Glycosylated haemoglobin (HbA 1c )	7
FG	1
Body weight	1
Creatinine and estimated glomerular filtration rate (eGFR)	1
N-terminal pro B-type natriuretic peptide (NT pro-BNP)	1
Blood pressure	1
Patient reported outcome	7

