**6.7 BASELINE, TIME WINDOWS AND CALCULATED VISITS**

For serum creatinine and values based on upon this measurement such as eGFR, baseline will be defined as the mean of all available measurements from the screening visit until start of randomised trial medication. For all other endpoints, baseline will be defined as the last available measurement before start of randomised trial medication.

Since the protocol specifies, that all measurements are taken at visit 2 before any intake of trial medication, all measurements at the first day of drug intake are assumed to qualify as baseline assessments.

For randomised patients without any treatment intake: For serum creatinine and values based on upon this measurement such as eGFR, baseline will be defined as the mean of all available measurements from the screening visit until and including the day of randomisation. For all other endpoints, baseline will be defined as the last available measurement before or on the day of randomisation.

Measurements taken after the first intake of randomised trial medication will be considered on-treatment values if they have been obtained up to end of the parameter specific follow-up period as defined in [Table 6.7: 1](#) below and will be assigned to the randomised study drug for efficacy and safety analyses.

Measurements taken after the end of the endpoint specific follow-up period after the last intake of study drug will be considered post-treatment values.

On-treatment (for OC-OT analysis) or all post-randomisation (for OC-AD analysis) efficacy and safety measurements will be assigned to visits based on time windows around the planned visit dates. These time windows are defined based on the planned number of days after the date of first administration of study drug.

The time window for the first visit after randomisation starts on the day after the first intake of study drug. The midpoint between two on-treatment visits defines the end of a time window, with the midpoint being included in the time window of the preceding visit.

Table 6.7: 1 Time windows for post-baseline efficacy measurements scheduled for each on-treatment visit for the first 3 years

Visit number	Visit label	Planned days	Time window (actual days after baseline)	
			Start	End
Endpoints assessed at each on-site visit (e.g. creatinine / eGFR)				
2	Baseline A	1	NA	1
3	Week 4	29	2	57
4	Week 12	85	58	155
6	Week 32	225	156	295
8	Week 52	365	296	449
10	Week 76	533	450	617

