### **eGFR (CKD-EPI)cr slope of change from baseline**

Slope in change from baseline of eGFR (CKD-EPI)cr will be analysed by a random coefficient model allowing for random intercept and random slope per patient. The model will include the factors treatment, sex, geographical region, baseline LVEF, and status of DM as fixed effects and eGFR (CKD-EPI)cr at baseline (continuous), age (continuous), time and interaction of treatment by time and interaction of eGFR (CKD-EPI)cr at baseline (continuous) by time as linear covariates and allow for randomly varying slope and intercept between patients. The model will include all on-treatment change from baseline data.

Since the slope is run on the change from baseline data, the intercept will model the acute drop, whereas the long-term effect is modelled by the slope.

A plot of individual patient slopes and separately of individual patient intercepts will be provided per treatment and by eGFR at baseline.

Subgroup analyses as outlined in Section 6.4 will be explored for eGFR slope. The subgroup model will include additionally to the model described above, the subgroup if not already part of the model, subgroup by treatment and subgroup by treatment by time. If the subgroup variable is a categorization of a continuous covariate, this covariate will be dropped from the subgroup model.

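### Should the confirmatory eGFR slope also be fitted without values taken during temporary drug interruptions?

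*SAP*

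**What the plan says.** SAP Section 7.5.1.1 fits a random intercept and slope model to change from baseline in eGFR. On the data it says: "The model will include all on-treatment change from baseline data". Protocol Section 7.5 agrees: "all available on-treatment change from baseline data will be used". The SAP gives the purpose of the two parameters: "the intercept will model the acute drop, whereas the long-term effect is modelled by the slope".

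The window is defined in three places:

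- SAP 6.6.1: "defined as time from first drug intake until last permanent treatment stop date plus the endpoint specific follow-up time".
- SAP 6.7: values after first intake "will be considered on-treatment values if they have been obtained up to end of the parameter specific follow-up period".
- SAP Table 6.1:2: for creatinine and eGFR, 1 day after last intake.

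Interruptions are foreseen. SAP 6.1 says "patients are allowed to go off-treatment and subsequently re-start treatment", and Table 6.1:1 describes the interval between stop and restart as "During Treatment interval, but not on treatment". Protocol 3.3.4.1 sets no time limit on a restart.

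The slope is the third test in the hierarchy, with alpha 0.001 at the final analysis. SAP 7.4.2 lists nine sensitivity analyses for the primary endpoint, and 7.5.1.1 lists seven for recurrent HHF. For the slope, 7.5.1.1 plans only plots of individual slopes and intercepts, and subgroup analyses.

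**The concern.** The SAP describes the same days as off treatment in Table 6.1:1 and counts them as on treatment for the slope. An eGFR value 2 days after a permanent stop is dropped, while one taken months into a gap that ends in a restart is kept.

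Protocol 1.2.3 reports that the initial eGFR fall on empagliflozin reversed once the drug was stopped. A rebound during a gap is thus acute change arriving partway through follow-up. A straight line can absorb part of it into the slope, which is supposed to carry only the long-term effect. At stake is the size, and possibly the significance, of a hierarchy-tested result whose alpha passes to the meta-analyses if the test succeeds.

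**Working it through.** **1. Do the definitions agree?** Yes. SAP 6.6.1 closes the window at the last permanent stop. SAP 6.7 and Table 6.1:2 close it after the last intake. For a patient who restarts, all three leave the gap inside the window. SAP 6.7 cites Table 6.7:1 for the follow-up period, although the days stand in Table 6.1:2; this is a clerical slip that does not alter the reading.

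**2. Does another planned analysis cover this?** No. The eGFR MMRM in SAP 7.6 uses OC-OT (the same window) or OC-AD (which adds off-drug data). The summaries of last on-treatment and follow-up values measure the reversal but do not re-estimate the slope. The repeat in patients with 52 weeks of exposure excluding gaps selects patients and removes no eGFR values.

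**3. Direction in one patient.** Visits fall on days 29, 85, 225, 365, 533, 701, 869 and 1037. In years the mean is 1.316 and the sum of squared deviations is 7.128. If eGFR is R higher at one gap visit at time t, the least-squares slope moves by R × (t − 1.316) / 7.128. With R = 3 (assumed):

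- gap at week 4: 3 × (0.079 − 1.316) / 7.128 = −0.52 mL/min/1.73 m² per year;
- gap at week 148: 3 × (2.839 − 1.316) / 7.128 = +0.64 per year.

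Early gaps lower the empagliflozin slope, late gaps raise it, and a constant off-drug share over time gives zero.

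**4. Direction in the arm.** If the off-drug share rises linearly from 0 to 10% at week 148, the mean slope moves by R × 0.10 / 2.839. That is +0.07 for R = 2 and +0.106 for R = 3.

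**5. Size in the planned model.** The documents give no figures for interruption frequency, timing or length, for the SDs, or for the rebound in this population, so all of these are assumed:

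- 1800 patients per arm (half of the approximately 3600 in SAP 9.6), scheduled visits only;
- follow-up 20–38 or 6–38 months; permanent stops 8% per year;
- one gap of 4–12 or 8–32 weeks in 10% or 30% of patients, with a restart inside the window;
- immediate rebound of 2 or 4 in the empagliflozin arm only;
- SDs 5 (intercept), 4 per year (slope) and 7 (residual).

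Projecting the gap values on intercept and time by generalised least squares gives these shifts in the slope difference, in mL/min/1.73 m² per year:

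| Gap timing | 10% with a gap | 30% with a gap |
|---|---|---|
| Early (mean start 8 weeks) | −0.127 to −0.038 | −0.382 to −0.120 |
| Even | +0.001 to +0.013 | +0.003 to +0.045 |
| Late (rising with time) | +0.011 to +0.037 | +0.027 to +0.110 |

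The standard error (SE) of the slope difference is 0.196 to 0.240.

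**6. In SE units.** Dividing by the smallest SE gives upper bounds:

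- late gaps: 0.037 / 0.196 = 0.19 at 10% and 0.110 / 0.196 = 0.56 at 30%;
- even gaps at 30%: 0.045 / 0.196 = 0.23.

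With each shift matched to the SE of its own setting, the maxima are 0.17 and 0.49 for late gaps, 0.18 for even gaps at 30%, and about 0.6 (10%) and 1.8 (30%) for early gaps. The early-gap shifts are negative, so they count against empagliflozin.

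**7. Effect on the test.** Two-sided alpha 0.001 has critical value 3.29, which leaves 0.0005 in the favourable tail. A favourable bias of 0.19 SE makes this P(Z > 3.29 − 0.19) = 0.0010. A bias of 0.56 SE makes it P(Z > 3.29 − 0.56) = 0.0032.

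**The case for a change.** The case for adding an analysis is reasonable. The slope is confirmatory, yet the SAP states an estimand only for the primary endpoint (7.4), so keeping gap values is not explained. The off-treatment dates are already needed for Table 6.1:1 and for exposure method b in 7.7. Excluding gap values in both arms would raise the SE by at most 2.5% under the assumed inputs. In a mixed-model check with 30% of patients having long gaps, exclusion reduced the shift from −0.43 to −0.03 (early gaps) and from +0.11 to +0.02 (late gaps).

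The facts in this stand, and so does the point that a reader may want to see the second fit. It does not show that the plan gives a wrong answer:

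- The word permanent in 6.6.1 already says that temporary stops do not close the window. A general definition in Section 6 need not be repeated in 7.5.1.1.
- Counting through interruptions and cutting at final stop is a recognised choice. The SAP handles adverse events the same way (7.8.1.1).
- Having nine and seven sensitivity analyses elsewhere does not make none a defect here.
- The second fit would not settle the matter. It removes values according to a post-randomisation event. Protocol 4.2.1 names acute illness and surgery as occasions for a temporary stop, and illness can change creatinine in either arm. A difference between the two fits could reflect rebound, illness or selection. The mixed-model check recovers the slope only because its gaps are unrelated to renal state.

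**Conclusion.** The observation is correct, but no change is needed. The plan makes a fair trade-off: it keeps every scheduled value up to the final stop, at the price of some off-drug values in patients who restart.

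The documents fix neither the size nor the direction of any effect. Under the assumed inputs, the shift in empagliflozin's favour is at most about 0.2 SE if 10% of patients have a gap and about 0.5 to 0.6 SE if 30% do. Even then the chance of a false favourable result stays near 0.003. The larger shifts need early, long gaps with a full, immediate rebound, and they cost power without creating a false claim. Illness-related change in eGFR during gaps is not modelled and could offset the rebound.

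A supplementary fit that drops eGFR values taken more than 1 day after the last dose before an interruption and before the restart date could be reported if wanted. It would be optional and would leave the confirmatory test and its alpha as they are.

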#### Observed case including data after treatment discontinuation (OC-AD):

All available data are considered, including values obtained on treatment or post-treatment.

Measurements are assigned to planned weeks according to [Table 6.7: 1](#).

As described in [Section 4](#), for patients that completed the treatment phase as planned (primary reason for end of treatment being completion of treatment period according to protocol), measurements after last study drug intake should not be considered. Therefore for those patients, any data after the endpoint specific follow-up time (as defined in [Table 6.1:2](#)) will not be included in the OC-AD analysis.

#### KCCQ imputation

If not otherwise noted, for endpoints of KCCQ scores, for patients who die, a worst score (score of 0) will be imputed for the score at all subsequent scheduled visits after the date of death where the score would have been assessed.

#### Multiple imputations:

A multiple imputations approach will be considered to impute missing data. Multiple imputation approaches taken are further specified in [Section 7](#) with the planned sensitivity analyses.

#### Imputation of missing covariates in multivariate Cox regression models and for recurrent event analyses

To avoid excluding patients from Cox regression analyses due to missing covariates, the overall population median of the corresponding variable will be imputed for continuous covariates and the most frequent category will be imputed for categorical covariates. No imputation will be done for covariates included in treatment by subgroup interaction terms.

